#### 7.4 What are the Adverse Events Associated with Transfusion?

There are a number of complications related to transfusion that are associated with considerable morbidity and mortality. Non-infectious risks from transfusion such as transfusion related acute lung injury (TRALI), which tends to occur more frequently in patients having cardiac surgery, perhaps because of increased systematic and pulmonary inflammation with cardiac surgery, has a high case fatality rate, 5 to 13%. Additionally, administrative errors resulting in hemolytic transfusion reactions can be life-threatening. Pulmonary edema, due to the volume of RBCs occurs more frequently in patients with critical illness and cardiovascular disease transfused at a Hb of 100 g/L compared to a Hb of 70 g/L8. Although the risk of acquiring transfusion transmitted viruses is low, new emerging pathogens constantly threaten the blood supply. Unnecessary transfusions also have an impact on the care of patients. Optimum utilisation of blood components is essential as there is a continuous strain on blood systems because of increased blood utilisation. Additionally, increased transfusion results in increased resource utilisation and the cost of blood is increasing40. In an era where there are new emerging pathogens and blood shortages, it is essential for patients to be transfused appropriately.

#### 7.5 What Systemic Reviews Have Been Conducted in Cardiac Patients?

Our recently published meta-analysis of 13 RCTs comparing restrictive and liberal transfusion strategies in patients undergoing cardiac surgery demonstrated that restrictive transfusion strategies did not result in an overall increased risk of anaemia-induced, tissue hypoxia-associated events. The risk ratio (RR) of mortality from 4545 patients assigned to a restrictive transfusion strategy and 4547 transfused according to a liberal strategy was 0.96 (95% CI 0.8, 1.2), myocardial infarction RR 1.0 (95% CI 0.8, 1.3), renal failure RR 0.96 (95% CI 0.8, 1.2), stroke 0.93 (95% CI 0.7, 1.3), or infection RR 1.1 (95% CI 0.98, 1.3). We are unaware of any meta-analyses specifically evaluating the effect of age and transfusion strategies. However, in our meta-analysis, the risk ratios for mortality, stroke and infection were all numerically higher with restrictive transfusion in paediatric studies.

The lack of well conducted randomised controlled trials evaluating the effect of age as well as the suggestion of increased risk associated with restrictive transfusion strategies in younger patients further substantiates the need for this RCT.

# 7.6 What Randomised Controlled Trials are being Conducted Addressing Haemoglobin Thresholds in Cardiac Surgery According to Age?

TRICS III and TITRe2 were recently completed and compared restrictive and liberal transfusion strategies. TITRe2, a superiority trial, randomised 2003 cardiac surgical patients with a postoperative Hb <90 g/L to receive RBC transfusions to maintain a Hb of >75 g/L or >90 g/L. A statistically significant difference was not apparent in the primary composite outcome of infection and ischemic events three months after surgery (35.1% in the restrictive group and 33.0% in the liberal group odds ratio, 1.1 (95% CI 0.9, 1.3)); but there was a 1.6% absolute difference in the secondary outcome of 90-day

mortality favouring the liberal strategy. Subgroup analysis according to decades of age was not conducted 30.

Although TRICS III established non-inferiority of the restrictive transfusion strategy in the 4860 patients analysed (Hb <75 g/L intraoperatively and postoperatively, or a liberal strategy of RBC transfusion for Hb <95 g/L intraoperatively and postoperatively while in an intensive care unit (ICU), and <85 g/L on a non-ICU ward), a trend of poorer outcomes with a restrictive strategy in younger patients was demonstrated as described above.

No other trials assessing the effect of age on transfusion thresholds in cardiac surgery are listed on clinicaltrials.gov.

#### 7.7 Why is a Trial Needed Now?

If restrictive transfusion strategies in younger cardiac surgery patients are associated with harm, a trial is needed to ensure that these patients are transfused according to the appropriate threshold. If younger patients are not experiencing harm from restrictive transfusion strategies, they should not be exposed to the morbidity and mortality of transfusions if transfused unnecessarily.

#### 7.8 Hypothesis

A higher Hb concentration for RBC transfusion (liberal transfusion strategy) will be superior to a restrictive strategy in terms of vital organ function (heart, brain and kidney) and mortality 6 months after cardiac surgery.

#### 8. Trial objectives

#### 8.1 Primary Objective

The primary objective is to determine whether a liberal RBC transfusion strategy is superior to a restrictive strategy in terms of vital organ function (heart, brain and kidney) and all-cause mortality 6 months after surgery.

#### 8.2 Secondary Objectives

The secondary objectives are to determine whether the liberal strategy is superior to a restrictive strategy in terms of:

- 1. Incidence of each individual component of the primary outcome: all-cause mortality, myocardial infarction, new onset renal failure requiring dialysis, and new focal neurological deficit (stroke) within 6 months
- 2. Composite and individual all-cause mortality, myocardial infarction, new onset renal failure requiring dialysis, and new focal neurological deficit (stroke) with index hospitalisation or after 28 days postoperatively, whichever comes first
- 3. Length of stay in the Intensive Care Unit (ICU) and hospital (index hospitalisation)
- 4. Prolonged low output state defined as the need for two or more inotropes for 24 hours or more, intra-aortic balloon pump or ventricular assist device postoperatively (index hospitalisation)
- 5. Duration of mechanical ventilation (index hospitalisation)
- 6. Infection: defined as septic shock with positive blood cultures; pneumonia defined as autopsy diagnosis or roentgenographic infiltrate and at least two out of three of the following criteria: fever, leukocytosis, and positive sputum culture; and/or deep sternal or leg wound infection requiring intravenous antibiotics and/or surgical debridement (index hospitalisation)

Page **21** of **55** 

IRAS ID: 325425

- 7. Acute kidney injury (AKI), defined by the Kidney Disease Improving Global Outcomes (KDIGO) clinical practice guideline  $^{46}$  a 50% increase in serum creatinine within 1 week or a 26.5  $\mu$ mol/L increase within 48 hours (index hospitalisation)
- 8. Delirium, based on one of the following criteria: Confusion Assessment Method (CAM) or CAM-ICU (even on 1 occasion), or Intensive Care Delirium Screening Checklist (ICDSC) > 3, or 3D-CAM, or 4AT ≥4, or more than one dose of haloperidol or similar antipsychotic drug, or documented delirium by neurologist or neurosurgeon or psychiatrist consultation (index hospitalisation)
- 9. Gut infarction confirmed by imaging (e.g. angiography), autopsy, or through surgical means (index hospitalisation)
- 10. Hospital visits (hospitalisation and/or emergency visits and coronary revascularisation at 6 months)
- 11. The proportion of patients transfused and the number of blood products utilised (RBCs, plasma, platelets) (index hospitalisation)
- 12. Seizures, defined as generalised or focal tonic-clonic movements consistent with seizure; or electroencephalogram demonstrating epileptiform discharges; or diagnosis of seizures by neurologist or neurosurgeon consultation (index hospitalisation)
- 13. Encephalopathy, defined as unexpected delayed awakening or severely altered mental status (unconscious despite no sedative medication for more than 5 days), or encephalopathy documented by neurologist or neurosurgeon or psychiatrist consultation (index hospitalisation)

## 9. Trial population

#### 9.1 Inclusion Criteria

- 1. ≥18 and ≤65 years of age
- 2. Planned cardiac surgery using cardiopulmonary bypass
- 3. Informed consent obtained
- 4. Preoperative European System for Cardiac Operative Risk Evaluation (EuroSCORE I) of 6 or more (using the standard additive EuroSCORE I available at www.euroscore.org/calcold.html or refer to the trial Manual of Operations)\*

\* The EuroSCORE criteria must be met prior to randomisation. If the EuroSCORE changes prior to randomisation due to a decision to change the type of procedure, then the patient should not be randomised. If the EuroSCORE changes after randomisation due to a decision to change the type of procedure (e.g. while in the OR), then the patient will continue to follow the protocol and will not be excluded.

#### 9.2 Exclusion Criteria

- 1. Patients who refuse participation
- 2. Patients who are unable to receive or who refuse blood products
- 3. Patients who are involved in a preoperative autologous pre-donation program
- 4. Patients who are having a heart transplant or having surgery solely for an insertion of a ventricular assist device
- 5. Pregnancy or lactation (a negative pregnancy test must be obtained prior to randomisation for women of childbearing potential)

Page 22 of 55

IRAS ID: 325425

## 10. Trial design

#### 10.1 Trial Overview

TRICS IV is an international, multi-centre, open-label, randomised controlled trial of two commonly used RBC transfusion strategies in higher risk patients ≤65 years of age having cardiac surgery, using a superiority trial design.

#### 10.2 Internal pilot

To assess whether the target number of UK centres; 18 within 9 months of green light, and recruitment rate 1 participant/site/month, will be achieved we will undertake a **9 month** internal pilot. Using the range of 0.74 to 1 participant/site/month, and 2 new sites set up per month as described above, we can specify two progression criteria (see table below). Targets for both criteria need to be met to achieve the following traffic light system:

Green: Proceed;

Amber: Amend, consult;Red: Discuss with funder.

The Trial Steering Committee in consultation with the funder will determine progression. The internal pilot will also be used to refine and amend recruitment strategies where needed, to ensure the sample is representative of the diversity of the UK population, and to test and refine the resource use questionnaire and frequency in collecting such data for the health economic analyses.

Progression criteria	Red	Amber	Green	
Recruitment rate (n/site/month)	<0.74	0.74-1	>1.0	
Number of sites opened	<14	14 - 18	>18	
If met will result in the following:				
Total number of participants recruited (9m pilot)	<66	66-89	>89	
No. months (total) to reach UK target (n=320)	>28	22-28	22	
Threshold (% of target participants recruited in pilot)	<74%	74-100%	100%	

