	8. Delirium, based on one of the following criteria: Confusion Assessment Method (CAM) or CAM-ICU (even on 1 occasion), or Intensive Care Delirium Screening Checklist (ICDSC) >3, or 3DCAM, or 4AT ≥4, or more than one dose of haloperidol or similar antipsychotic drug, or documented delirium by neurologist or neurosurgeon or psychiatrist consultation (index hospitalisation).		
	9. Gut infarction confirmed by imaging (e.g. angiography), autopsy, or through surgical means (index hospitalisation).		

Page **13** of **55** IRAS ID: 325425

	10. Hospital visits (hospitalisation and/or emergency visits and coronary revascularisation at 6 months).				
	11. The proportion of patients transfused and the number of blood products utilised (RBCs, plasma, platelets) (index hospitalisation).				
	12. Seizures, defined as generalised or focal tonic-clonic movements consistent with seizure; or electroencephalogram (EEG) demonstrating epileptiform discharges; or diagnosis of seizures by neurologist or neurosurgeor consultation (index hospitalisation).				
	13. Encephalopathy, defined as unexpected delayed awakening or severely altered mental status (unconscious despite no sedative medication for more than 5 days), or encephalopathy documented by neurologist or neurosurgeon.				
Trial population	Patients at moderate to high risk of death (EuroSCORE I ≥ 6) that are 65 years of age or younger undergoing cardiac surgery on cardiopulmonary bypass (CPB).				
Trial design	Multi-centre, open-label, randomised controlled trial of a restrictive versus liberal transfusion strategy in higher risk patients ≤65 years of age having cardiac surgery on cardiopulmonary bypass, using a superiority trial design. A health economic analysis is embedded in the UK arm of the trial.				
	In the UK, an internal pilot including progression criteria has been built in, to assess whether the target number of UK centres within 9 months of green light, and recruitment rate of one participant per site per month, can be achieved.				
International sample size	1760 randomised participants in ~72 international sites.				
UK sample size	320 participants (160 per group) in 22 UK cardiac centres.				
Randomisation	Randomisation will have a 1:1 ratio, will be based on random permuted blocks of varying sizes, and will be stratified by centre and age.				

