**Outcomes:** The primary outcome is a composite of any of the following events within 6 months of the initial surgery: 1. All-cause mortality or 2. Myocardial infarction as defined by the 4th universal definition of myocardial infarction or 3. New onset renal failure with dialysis or 4. New focal neurological deficit (stroke). Secondary outcomes will include costs, quality of life, cost-effectiveness, and safety. Process and adherence will be monitored.

**Internal Pilot:** Planned site set-up and recruitment targets (1 participant/ site/ month), as well as methods for collection of healthcare resource use, will be tested in a 9 month internal pilot with prespecified Stop/ Go criteria.

**Sample Size:** The trial is powered to detect a Risk Ratio of 0.70 between groups at six-months. To achieve 90% power with  $\alpha$  =0.05, and with adjustment for an expected attrition rate of 4.5% and a single interim analysis, 1,802 participants (901 per group) are required.

Page **15** of **55** IRAS ID: 325425

**Analysis:** will follow a pre-specified statistical analysis plan in the intention to treat population. A cost utility analysis will be performed.

**Project timetable:** Start date: 1st February 2023. Months 1-7 set-up, months 8-30 recruitment, months 30 to 35 follow-up, months 34 to 36 data cleaning, site closedown.

**Dissemination:** We use the Knowledge Framework to focus on knowledge creation and dissemination to key stakeholders, including participants, clinicians, service users and commissioners.

Page **16** of **55** 

IRAS ID: 325425

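### UK internal pilot: hitting the stated target exactly (18 sites, 1 participant/site/month) is rated amber, and the planned opening rate ends one site short of green

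*Protocol*

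**What the plan says.** Section 10.2 gives the target that the pilot is meant to test: "To assess whether the target number of UK centres; 18 within 9 months of green light, and recruitment rate 1 participant/site/month, will be achieved". The Protocol summary (section 4) repeats the rate target: "recruitment rate of one participant per site per month, can be achieved". The Scientific abstract (section 5) says that set-up and recruitment targets "will be tested in a 9 month internal pilot with prespecified Stop/ Go criteria".

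The planning assumptions behind the table are given as "Using the range of 0.74 to 1 participant/site/month, and 2 new sites set up per month as described above". The combination rule is "Targets for both criteria need to be met to achieve the following traffic light system".

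The two criteria rows of the table read, as red / amber / green:

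- Rate: "Recruitment rate (n/site/month) <0.74 0.74-1 >1.0".
- Sites opened: <14 / 14-18 / >18.

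Three rows then show what follows if the criteria are met:

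- Participants recruited in the pilot: <66 / 66-89 / >89.
- Months to the UK target of 320: >28 / 22-28 / 22.
- Percentage of the pilot target recruited: <74% / 74-100% / 100%.

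Green means proceed, amber means amend and consult, and red means discuss with the funder. The Trial Steering Committee, consulting the funder, determines progression.

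**The concern.** A pilot that delivers its stated target should be rated green. Here the values named as the target are the upper ends of the two amber bands, and green starts strictly above them. The number of sites planned by month 9 also equals the top of the amber band, so good recruitment at the sites that open cannot lift the pilot to green.

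What is at stake is how clear a prespecified decision rule is. For the planned scenario the criteria rows say amber, the participants row says green, and two further rows allow either. The committee and funder would have to interpret the table after seeing the pilot data, which prespecification is meant to avoid.

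**Working it through.** **Inputs, all from section 10.2 unless noted.** Pilot length 9 months; two sites opened per month; target 18 sites; rates 0.74 and 1 participant/site/month; UK target 320 participants (also section 4); 22 UK centres planned (section 4).

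**Step 1: reproduce the table's own figures.** Let two sites open at the start of each month and hold the number at 18 after month 9.

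- Sites at month 9: 2 x 9 = 18.
- Site-months in the pilot: 2 + 4 + ... + 18 = 90.
- Participants = rate x 90. Months to 320 = 9 + (320 - rate x 90)/(18 x rate).

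| Quantity | At 1.0 | Printed green | At 0.74 | Printed boundary of amber and red |
|---|---|---|---|---|
| Participants in pilot | 1.0 x 90 = 90 | >89 | 0.74 x 90 = 66.6 | 66 |
| Months to 320 | 9 + 230/18 = 21.8 | 22 | 9 + 253.4/13.32 = 28.0 | 28 |
| % of pilot target | 90/90 = 100% | 100% | 66.6/90 = 74% | 74% |

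Counted in whole months at 1.0, recruitment stands at 90 + 13 x 18 = 324 in month 22, the first month in which 320 is passed. Opening sites mid-month gives 81 site-months and at month end 72. Neither reproduces 90 or 66.6. The derived rows therefore rest on 18 sites, with green at a rate of 1.0.

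**Step 2: rate that same scenario with the table.**

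| Row | On-plan result | Rating as printed |
|---|---|---|
| Sites opened | 18 | amber (14-18) |
| Rate | 1.0 | amber (0.74-1) |
| Participants | 90 | green (>89) |
| Months to 320 | 22 | amber (22-28) and green (22) |
| % of pilot target | 100% | amber (74-100%) and green (100%) |

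**Step 3: what green would take.** More than 18 sites means at least 19. Over nine months that is 19/9 = 2.11 openings a month against the planned 2. Because both criteria must be met, a higher recruitment rate cannot compensate.

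**Step 4: do the derived rows fit the amber floor?** Open 14 sites at two a month, then hold. Site-months are 2 + 4 + ... + 14 + 14 + 14 = 84. At 0.74 this gives 0.74 x 84 = 62.2 participants, and months to 320 = 9 + (320 - 62.2)/(14 x 0.74) = 9 + 24.9 = 33.9. Both are red in the derived rows (<66; >28), although both criteria are amber. The printed 66 and 28 belong to 18 sites at 0.74, not to 14. This limits what a repair of the derived rows can claim.

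**The case against.** The strongest case on the other side is that the consequence is small. The committee and funder decide, amber is not a stop, and people shown 18 sites, a rate of 1.0, 90 participants and 100% of target would recognise a pilot on plan. That stands, and it limits the weight of the point.

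A reader might infer that green cannot be reached at all. The document does not support that. Two a month is a planning figure, nothing caps openings at 18, 22 UK centres are planned, and section 22.1 reports that all 22 units were willing to take part. Green is missed only at the planned opening rate, and by one site.

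A reader might also infer that all three derived rows contradict the criteria rows. Only the participants row clearly does so. The months and percentage rows are ambiguous, because 22 months and 100% are printed in both bands.

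Nor is this a miscalculation. The table's arithmetic reproduces, and the fault lies in strict rather than inclusive cut-offs.

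The sponsor could say that a bar above target was intended. The green consequences argue against this, since they are computed from 18 sites at 1.0 and not from anything higher.

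Finally, the decision may already have been taken. Section 5 starts recruitment in month 8 of a project beginning 1 February 2023, so on schedule a nine-month pilot would end around May 2024, before version 2.0 of 16 August 2024. The protocol does not say whether progression was decided. Version 2.0 did, however, amend these same criteria (section 24.3), so they were treated as current.

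**Conclusion.** The point holds as a boundary inconsistency. The two binding rows rate the stated target amber, and the planned set-up rate ends one site short of green (18 against at least 19, or 2 against 2.11 openings a month). The table's green consequences describe exactly that on-target pilot: 90 participants is green, while 22 months and 100% each sit in two bands.

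This rests on the section 10.2 figures, with sites opening at the start of each month and held at 18 after month 9, the only one of the three opening conventions tried that reproduces the printed totals. The effect is limited to UK progression: an on-plan pilot is classed as needing amendment and consultation. It would be wrong to infer that such a pilot would be stopped, or that the trial's allocation, endpoint, power, type I error or patient safety is affected. Nothing in the protocol links this table to any of them. It should be corrected because it is a prespecified threshold that does not match its own target.

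**What to change.** Edit the table in section 10.2:

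- **Sites opened:** green at least 18; amber 14-17; red below 14.
- **Recruitment rate:** green at least 1.0; amber 0.74 to below 1.0; red below 0.74.
- **Months to 320:** green 22 or fewer; amber more than 22 and up to 28; red more than 28.
- **% of pilot target:** green 100% or more; amber 74% to below 100%; red below 74%.
- **Participants:** the printed bands do not overlap and can stay.
- **Label the three derived rows** as illustrative for 18 sites opened at two a month, so that they are not read as further criteria. Without the label, a pilot with 14 sites at 0.74 would be amber on both criteria and red on participants and months.

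With these limits the on-plan pilot is green on every row. The cost is one table edit and a label in the next UK amendment, with no effect on patients or on the analysis. If progression has already been decided, a note recording how the boundary was read would serve the same purpose.

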#### 10.3 Randomisation Procedure

Randomisation will be performed by the delegated research nurse/enroling physician using a centralised web-based system (REDCap) generated by the Applied Health Research Centre (AHRC) at the Li Ka Shing Knowledge Institute of St. Michael's Hospital, Unity Health Toronto. UK sites will use this system to enter relevant data to enable randomisation of participants in the UK. Access to the randomisation system will be managed by the AHRC following completion of necessary training.

Randomisation will have a 1:1 ratio, will be based on random permuted blocks of varying sizes, and will be stratified by centre and age. We will use web-based electronic case report forms (eCRFs), which can be accessed by each site, to randomly allocate participants to interventions. Each participant will be assigned a unique participant ID at enrolment. This unique participant ID will be used to identify the individual participant throughout the trial and will not be reassigned to any other participant.

Whenever feasible, randomisation will occur no more than 24 hours prior to the scheduled surgery to minimise the risk of losing randomised patients due to unplanned surgery cancellations. This timeline is only a guideline and it is not considered a protocol deviation to randomise > 24 hours before surgery.

Page 23 of 55

IRAS ID: 325425

